Opioid-related overdose deaths have quadrupled since 1999 making drug overdose the new leading cause of accidental death in the U.S.¹ The current practice of providing emergency department (ED) patients who endorse opioid use disorder (OUD) with only a referral to local treatment programs, which often have long waiting lists, represents a tragic missed opportunity to engage patients in sustained medical care.^{2,3} We hypothesize that a novel intervention at the UVM Medical Center (UVMMC), which will 1) initiate buprenorphine treatment in patients presenting at the ED with OUD, and 2) guarantee enrollment in the UVMMC Addiction Treatment Program (ATP) within 24 to 72 hours, will address the acute crisis period when individuals are most vulnerable to relapse and lead to increased long-term participation in Medication-Assisted Treatment (MAT). This project is expected to generate immediate benefits for those enrolled and will provide proof of concept evidence for a new model of engaging individuals with OUD in long-term care.

Vermont has a lower rate of fatal opioid overdoses than the national average and a significantly lower rate than other rural New England states (e.g. 13.9 deaths per 100,000 in Vermont compared to 26.2 in New Hampshire in 2014).⁴ This situation has been attributed to the development of an effective "Hub and Spoke" OUD treatment system and proactive state-sponsored programs to increase access to emergency opioid overdose rescue kits and needle exchanges.^{4,5} Despite this, the number of drug-related fatalities in Vermont continues to increase in parallel with the alarming national upward trend, surging 37% from 2015 to 2016.⁶ Thus, the Vermont response to the opioid epidemic urgently requires further improvement to address a still growing problem. A key challenge in addressing OUD is that most individuals who would benefit from a medical intervention do not receive any assistance. Only 10.8% of the estimated 21.7 million people in the U.S. with a past year substance use disorder received specialized treatment.⁷ Consequently, the presentation of patients with OUD at the ED is a critical

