Objectives: Clearly state the primary and secondary objective(s) of the study.

The primary outcome will be urine specimens for illicit opioids at 1 week and 3 & 6 months after ED initiated treatment. Urine specimens will be collected under observation of same-sex staff and immediately analyzed for opioids (buprenorphine, methadone, oxycodone, hydrocodone, hydromorphone, heroin, fentanyl) and other drugs (cocaine, amphetamines, benzodiazepines, cannabinoids) via enzyme multiplied immunoassay. Missing urine specimens will be considered positive for illicit opioids, consistent with an intent-to-treat approach.

[figure not shown]
Secondary outcomes will include self-reported illicit opioid or other (non-opioid) drug use, treatment enrollment status and behavioral questionnaires (i.e. the GPRA Client Outcome Measures questionnaire, the Treatment Effectiveness Assessment (TEA),⁴³ and the Vermont Treatment Needs Questionnaire (TNQ)²¹).

METHODS AND PROCEDURES

Study Design: Describe the research design, including a description of any new methodology and its advantage over existing methodologies.

This pilot project will test whether ED-initiated buprenorphine treatment for individuals presenting to the UVMMC ED with OUD combined with a MAT bridge clinic leads to a reduction in illicit opioid use at 1 week, and 3 & 6 months compared ED-initiated treatment with a direct referral to a local MAT provider. The intervention and study design include 5 main stages (see figure below): 1) Patients admitted to the ED with indicators of OUD will be consented and screened for study eligibility; 2) Participants will undergo buprenorphine induction at the ED; 4) Participants enrolled at Central Vermont Medical Center and Porter Medical Center will be referred directly to a local MAT provider. Participants enrolled at UVMMC will be referred to the UVMMC ATP, a MAT bridge clinic that will supervise MAT with buprenorphine in all participants who enroll in the program until the individual is transferred to a long-term MAT provider, referred to a higher level of care or drops out of treatment --treatment duration at ATP is typically 8 weeks before referral of stable patients to primary care providers; 5) All participants will be contacted at 1 week, and 3 & 6 months after randomization to determine current illicit opioid use.

We expect to enroll 200 participants over 3 years.

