Part 5) Outcome Assessment. The primary outcome will be illicit opioid use at 1 week and 3 & 6 months after buprenorphine induction. Consistent with standard ATP practice, urine sample collection and analysis will be performed by Aspenti Labs (<https://www.aspenti.com/>), a clinical drug testing service which is open Monday to Friday 7AM-7PM and has multiple locations throughout Vermont. Urine specimens will be collected under observation of same-sex staff and analyzed for opioids (buprenorphine, methadone, oxycodone, hydrocodone, hydromorphone, heroin, fentanyl) and other drugs (cocaine, amphetamines, benzodiazepines, cannabinoids) via enzyme multiplied immunoassay. Missing urine specimens will be considered positive for illicit opioids, consistent with an intent-to-treat approach. Additional outcomes will include self-reported illicit opioid or other (non-opioid) drug use, treatment enrollment status and behavioral questionnaires (i.e. the GPRA Client Outcome Measures questionnaire to track self-reported drug-use and life conditions). The Treatment Effectiveness Assessment (TEA)⁴³ will be included at 1 week, 3 months and 6 months to track patient perception of treatment progress. Additional follow-up questions based on the PhenX toolkit are attached.

Retention. Participating in OUD treatment has health advantages for the participants which is a motivation to remain in the study. Participants will receive a \$25 gift card after answering questionnaires in Step 11. In addition, as an incentive to provide a urine sample and answer questions at follow-up, participants will receive a \$25 gift card for answering questions by phone and a \$50 gift card for a urine sample at each of the three outcome time points completed (i.e. 1 week, 3 and 6 months post randomization). In total, participants can earn up to \$250 for their participation in the study. To avoid altering the motivation to stay in MAT, participants will earn payment for providing the urine samples and answering questions at each of the 3 follow-up time points, regardless of whether they are currently in treatment. Missing urine specimens will be considered positive for illicit opioids, consistent with an intent-to-treat approach.

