Participants will be contacted by phone, text and/or email. A letter will also be mailed to participants (see attached). In the event the participant cannot be reached by any other means, a letter will be sent to the contact person provided by the participant at intake on the Locator Form. Contact information for phone, text and email will be collected at the initial ED visit. The dates (i.e. 1 week, 3 months and 6 months after randomization) for the follow-up visits will be written down and given to participants with other study materials during the initial ED visit. Participants will be contacted in the week before the follow-up visits at 3 and 6 months to remind them of the date and answer any question about where and how urine samples will be collected. Participants will also be reminded again the day before.

For research involving survey, questionnaires, etc.: Describe the setting and the mode of administering the instrument and the provisions for maintaining privacy and confidentiality. Include the duration, intervals of administration, and overall length of participation. (describe and attach all instruments)

Not applicable

Behavioral questionnaires will be used to assess participants at the following time points.

At baseline, participants will be assessed using the Locator Form, Referral, Suicidality, GPRA, MINI Neuropsychiatric Interview, Why are you enrolling in this program: Prevent overdose/Want to be sober/Family pressure/Legal pressure/Job pressure/Other. Total duration 1 hour.

At week 1, participants will be complete the MINI questionnaire Part II. Total duration 25 minutes.

At 3 months, participants will be assessed using a modified version of the PhenX drug use toolkit, the TEA and attached follow-up questionnaire and the GPRA. Total duration 25 minutes.

At 6 months, participants will be assessed using a modified version of the PhenX drug use toolkit, the TEA and attached follow-up questionnaire based on the PhenX toolkit Total duration 35 minute.

At 3 and 6 month follow-up:

1. Since you received buprenorphine (suboxone) in the ED have you taken any more buprenorphine prescribed for you by a doctor or other prescriber? (If No, skip to item 3)
2. If you answered yes to #1: are you currently (last 30 days) enrolled in treatment with a prescriber?
3. If you are not currently receiving suboxone from a prescriber, why?

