Follow up questionnaire (attached) based on PhenX drug use history toolkit takes approximately 105 minutes to complete TEA takes approximately 5 minutes to complete

The GPRA Client Outcome Measures questionnaire takes approximately 30 minutes to complete.

Baseline questionnaires will be administered on an iPad by the EMRAP staff or the study RA in patient care areas or by phone.

At 1 week, 3 months and 6 months, questionnaires will be administered by the study RA by phone. Participants may be contacted in advance by text or email to arrange a time for the call that is convenient for the participant.

Questionnaires will be labelled with the participant's unique study ID number and stored separately from identifiable information (e.g. name, address, phone number etc).

Statistical Considerations: Delineate the precise outcomes to be measured and analyzed. Describe how these results will be measured and statistically analyzed. Delineate methods used to estimate the required number of subjects. Describe power calculations if the study involves comparisons. Perform this analysis on each of the primary and secondary objectives, if possible.

200 hundred individuals will be recruited to the study over the course of 3 years.

The primary outcome measure will be illicit opioid use at 1 week and 3 & 6 months.. Group differences (i.e. with or without the MAT bridge clinic) in opioid use will be assessed by logistic regression at each of the three time points. A power analysis using G*Power50 indicates that a medium effect size, e.g. 0.3, related to the comparison of illicit opioid use in the experimental and control groups will be correctly identified with a power of 0.93 in a total sample of 200 individuals. Statistical tests will be performed in SPSS Statistics for Windows, Version 21.0. (Armonk, NY: IBM Corp). Logistic regression will be one-tailed with significance defined as $p < 0.05$.

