A subject may decline to join the study, or may withdraw from the study at any time. Subjects declining consent or withdrawing from the study will have all data deleted, with the exception of the logs that document the destruction. The study code assigned to the subject will remain in the database with "voluntarily withdrawn from the protocol" as the only information retained about the subject (patient identifiers will not be saved except on the study master list).

Note: Participants are not required to test negative on urine drug tests at the assessment time points of 1 week, 3 months and 6 months. It is expected that many will test positive. Although drug tests are part of the ATP treatment program, this is independent of observational urine drug tests performed for the study at 1 week, 3 months and 6 months which will be used to determine the success of the ED-initiated intervention. Individuals who decline or withdraw from ATP services are not automatically withdrawn from the research study. Additionally, individuals who withdraw or are withdrawn from the study may continue to seek treatment services from the ATP. Participation or not in the study will not affect medical care provided by ED or the ATP.

Sources of Materials: *Identify sources of research material obtained from individually identifiable human subjects in the form of specimens, records or data. Indicate whether the material or data will be obtained specifically for research purposes or whether use will be made of existing specimens, records or data.*

Urine samples, Questionnaires, Medical History

DRUG AND DEVICE INFORMATION

Investigators are encouraged to consult the UVM Medical Center Investigational Pharmacy Drug Service ([name]) prior to finalizing study drug/substance procedures.

*Investigational Pharmacy Drug Service was consulted. They determined that IDS will not be involved in the current study because Suboxone is not be investigated as an IND. Rather, the research investigates a novel method to increase treatment enrollment with an already established use of Suboxone.

Drug (s)

Not applicable

Drug name – generic followed by brand name and common abbreviations. Availability – Source and pharmacology; vial or product sizes and supplier. If a placebo will be used, identify its contents and source. (attach investigational drug brochure)

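### The only printed measure of treatment enrolment is phone self-report, and the buprenorphine and methadone results from the 3- and 6-month study urines are not used to corroborate it

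*Combined protocol and SAP*

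**What the plan says.** **Enrolment as an aim.** The opening summary hypothesises that the intervention will "lead to increased long-term participation in Medication-Assisted Treatment (MAT". Under Drug and Device Information the study is described again in those terms: "the research investigates a novel method to increase treatment enrollment with an already established use of Suboxone".

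**Enrolment as an outcome.** Objectives lists "treatment enrollment status and behavioral questionnaires" among the secondary outcomes, and Part 5) Outcome Assessment lists the same items as additional outcomes. Neither section says where enrolment status comes from or how it is defined. The primary outcome is a different quantity: "The primary outcome will be illicit opioid use at 1 week and 3 & 6 months after buprenorphine induction".

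**How enrolment is asked.** The questionnaire section prints two relevant items for 3 and 6 months. Item 1 asks whether, since the emergency department (ED) visit, "have you taken any more buprenorphine prescribed for you by a doctor or other prescriber? (If No, skip to item 3". Only those who answer yes reach item 2, "are you currently (last 30 days) enrolled in treatment with a prescriber". The mode is stated a little later: "At 1 week, 3 months and 6 months, questionnaires will be administered by the study RA by phone".

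**What the urine already provides.** Part 5 has observed specimens "analyzed for opioids (buprenorphine, methadone, oxycodone, hydrocodone, hydromorphone, heroin, fentanyl" and other drugs. The Biological samples paragraph gives the collection times as 1 week, 3 months and 6 months.

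**What is analysed.** Statistical Considerations gives one analysis, logistic regression of illicit opioid use at each time point. It gives none for enrolment and no use of the buprenorphine or methadone results in connection with enrolment.

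**The concern.** The protocol does not rely on self-report for drug use: observed urine is primary and self-reported use is secondary. Enrolment gets no comparable check, although the laboratory result that could supply one is obtained in both groups at the same two time points.

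Misreporting need not be equal between groups. Study Design assigns the follow-up pathway by site, and no blinding is described. The bridge-clinic group is placed with the UVMMC Addiction Treatment Program (ATP), whose psychiatrists are described under Data Safety and Monitoring as part of the study team. The comparison group goes to local providers. The Impact paragraph says that positive findings would support adoption across the network, so an enrolment result may be relied on even though it is secondary.

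Clinic records would not be an even substitute. They cover one group, and Study Design puts typical ATP treatment at 8 weeks before transfer, so many participants will have left by 3 months.

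**Working it through.** The plan has no enrolment rate, reporting accuracy, power or sample size for this outcome, so there is no figure to reproduce. The stated power of 0.93 concerns illicit opioid use and is not used here. All rates and accuracies below are assumptions.

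**Inputs from the documents.** Number of Subjects expects 140 participants at UVMMC and 200 in total, leaving 200 − 140 = 60 at the two referral sites. Statistical Considerations sets a one-sided 0.05 level for the primary analysis; it is borrowed here for illustration.

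**Step 1: overstatement of the rate.** Assume 60% report current treatment and a fraction f of those reports has no urine support. Overstatement = 0.60 × f.
- f = 0.10: 0.60 × 0.10 = 0.06, or 6 points (supported rate 54%).
- f = 0.20: 0.60 × 0.20 = 0.12, or 12 points (supported rate 48%).

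This treats every yes with a negative urine as a false report and ignores under-reporting.

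**Step 2: a real difference hidden.** If 60% report treatment in both groups, but 15% of reports in one and 5% in the other are unsupported, the supported rates are 0.60 × 0.85 = 51% and 0.60 × 0.95 = 57%. The reported difference is zero and the supported difference is 6 points.

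**Step 3: a false difference created, or a real one diluted.** With true rate p, sensitivity Se and specificity Sp, the observed rate is Se × p + (1 − Sp) × (1 − p). The one-sided rejection rate is Φ((Δ − 1.645 × SE0)/SE1), where SE0 is pooled, SE1 is unpooled, and the groups are 60 and 140.

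Example: p = 0.50 in both groups and Se = 0.95, with Sp 0.90 (referral) and 0.80 (bridge).
- Observed rates: 0.475 + 0.05 = 0.525 and 0.475 + 0.10 = 0.575, so Δ = 0.05.
- Pooled rate: (60 × 0.525 + 140 × 0.575)/200 = 0.56.
- SE0 = √(0.56 × 0.44 × (1/60 + 1/140)) = 0.0766.
- SE1 = √(0.525 × 0.475/60 + 0.575 × 0.425/140) = 0.0768.
- Φ((0.05 − 0.1260)/0.0768) = Φ(−0.99) = 0.16.

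Se is 0.95 in the table unless stated.

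| True rate, referral vs bridge | Reporting accuracy | Observed, referral vs bridge | Difference (points) | One-sided rejection |
|---|---|---|---|---|
| 50% vs 50% | Sp 0.90 in both | 52.5% vs 52.5% | 0 | 0.05 |
| 50% vs 50% | Sp 0.90 referral, 0.80 bridge | 52.5% vs 57.5% | +5 | 0.16 |
| 50% vs 50% | Sp 0.90 referral, 0.70 bridge | 52.5% vs 62.5% | +10 | 0.37 |
| 50% vs 50% | Sp 0.70 referral, 0.90 bridge | 62.5% vs 52.5% | −10 | wrong direction |
| 50% vs 50% | Se 0.80 in referral only, Sp 0.90 in both | 45.0% vs 52.5% | +7.5 | 0.25 |
| 50% vs 70% | no error | 50.0% vs 70.0% | +20 | 0.85 |
| 50% vs 70% | Sp 0.90 in both | 52.5% vs 69.5% | +17 | 0.74 |
| 50% vs 70% | Sp 0.70 in both | 62.5% vs 75.5% | +13 | 0.59 |

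The fifth row mimics methadone patients in the referral group being missed by the skip at item 1. The Purpose section describes methadone as a Hub treatment in the same system. A participant on methadone with no further prescribed buprenorphine is never asked item 2.

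The direction of any bias is therefore not known in advance. Equal error in both groups dilutes a real difference. Unequal error can move it either way.

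**The case against.** The strongest reply has four parts.

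1. **The source of enrolment is unstated, not declared to be self-report.** Sources of Materials lists medical history, a coordinator is placed at the ATP, and the attached questionnaires are not in the text. This stands as a limit on wording: one can say only that phone self-report is the sole measure printed. It does not remove the point, because medical history is nowhere tied to enrolment and further questionnaires would still be self-report.

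2. **Urine does not verify enrolment.** A positive result shows exposure. It does not show a prescriber, and it does not cover a 30-day window. Non-prescribed buprenorphine also tests positive. This stands, so the measure must combine report and urine and be described as corroboration. Full verification would need provider or prescription records.

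3. **The methadone half cannot work with the printed skip.** This also stands. The question has to change with the analysis.

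4. **Differential misreporting is speculative.** A study research assistant asks the questions, payment does not depend on being in treatment, and leaving the ATP does not end study participation. These features reduce the incentive to misreport. They do not show that reporting is equal in groups that differ by site and clinic.

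It is also true that no secondary outcome has an analysis plan. That is a wider gap, and it does not make this check less useful.

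**Conclusion.** The point holds as an inexpensive improvement to a secondary outcome. Enrolment is a stated target of the intervention, its only printed measure is phone self-report, and assay results that could corroborate it at 3 and 6 months have no planned use for that purpose.

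The size is unknown. Under the assumption of 60% reporting treatment and 10 to 20% of reports unsupported, the overstatement is 6 to 12 points. Under the assumed accuracies, differential error shifts the group difference by 5 to 10 points in either direction.

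Three stronger readings are tempting, and the documents do not support them.
- A reader might infer that the main result is compromised. It is not: Aim 1 and the primary outcome are illicit opioid use by urine.
- A reader might infer that 15% versus 5% over-reporting produces a spurious 6-point effect. With 60% reporting in both groups it hides a 6-point difference (51% vs 57%). A spurious gap requires equal true rates.
- A reader might infer that a positive urine would settle enrolment. It supports medication taking only.

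**What to change.** - State the source and definition of treatment enrolment status, and keep the self-reported rate.
- Put the enrolment question to all participants at 3 and 6 months and for any MAT, so that item 1 no longer skips methadone patients.
- Pre-specify a supportive measure at 3 and 6 months: reported in treatment and study urine positive for buprenorphine or methadone. Give the self-report by urine cross-table for each group.
- Label it as corroborating medication taking, not as proof of enrolment or of the 30-day window.
- Report it twice: among participants with both an interview and a urine, and with missing urine counted as not verified. Give the number missing per group. The existing missing-urine rule covers illicit opioids only. The phone interview and the urine are paid separately, so some participants will have one without the other.
- Do not apply it at 1 week, when the 3-day Starter Pack from the ED may explain a positive result.

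**Cost.** Protocol wording, one table and a small change to the skip pattern, with no new specimen or assay. The downside is that verified status is unavailable without a urine. If missingness differs by site it could bias the verified rate, which is why both versions and the counts are needed.

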4. Since you started receiving treatment in the ED have you experienced any of the following side effects of buprenorphine? (Constipation, diarrhea, stomach pain, nausea, vomiting, brain fog, sleeping too little, tiredness, sexual problems, feeling depressed or down, feeling anxious, headache)

If yes follow up with: How much discomfort did this cause you on a scale 1 to 5 where 1 is mild and 5 is severe?

5. Have you been doing more of any of the following since starting treatment in the ED:

Have you been eating more than before you started treatment?

Have you been drinking caffeine more than before you started treatment?

Have you been smoking more cigarettes or other nicotine products more than before you started treatment?

Have you been using more marijuana than before you started treatment?

Have you been drinking more alcohol than before you started treatment?

Have you been using other drugs more than before you started treatment? If yes, which ones?

Have you been spending more time online than before you started treatment?

Have you been gambling more than before you started treatment?

Have you been having more sex than before you started treatment?

Have you been exercising more than before you started treatment?

Any other activities? If yes, what are they?

6. How often over the last two weeks have you been bothered by not being able to stop or control how much you eat?

How often over the last two weeks have you been bothered by how much caffeine you drink?

How often over the last two weeks have you been bothered by how many cigarettes you smoke or use other nicotine products?

How often over the last two weeks have you been bothered by how much marijuana you use?

How often over the last two weeks have you been bothered by how much alcohol you drink?

How often over the last two weeks have you been bothered by how much other drugs you use? If yes, which ones?

How often over the last two weeks have you been bothered by how much time you spend online?

How often over the last two weeks have you been bothered by how much time spent gambling?

How often over the last two weeks have you been bothered by how much time spent having sex?

How often over the last two weeks have you been bothered by how much time spent exercising?

Individual questionnaire durations are as follows:

MINI Neuropsychiatric Interview takes approximately 15 minutes to complete.

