Biological samples. Urine samples will be collected at 1 week, 3 months, and 6 months. Urine specimens will be collected under observation of same-sex staff and immediately analyzed for opioids (buprenorphine, methadone, oxycodone, hydrocodone, hydromorphone, heroin, fentanyl) and other drugs (cocaine, amphetamines, benzodiazepines, cannabinoids) via enzyme multiplied immunoassay (Microgenics, Fremont, CA). Missing urine specimens will be considered positive for illicit opioids, consistent with an intent-to-treat approach.

Risks. The participants enrolled in this study have OUD. The most effective current treatment for the disorder is Medication-Assisted Treatment which will be provided to enrolled participants. The risks of participating in the study are weighed against sequelae of not seeking treatment, which include death due to acute overdose, birth defects in pregnant women and health risks related to needle sharing.

We will obtain careful informed consent to ensure that every potential participant fully understands all of the possible risks. In addition, we will not include individuals who we believe would not be able to tolerate the study procedures.

Medication related risks will be mitigated by medical supervision at the ATP who will train ED staff.

Risks from Buprenorphine (Suboxone):
Common side effects of Suboxone include:

- nausea;
- constipation or abdominal pain;
- sweating;
- tiredness or sleep other problems (insomnia);
- headache;
- redness, pain, or numbness in your mouth;
- feeling drunk; or,
- trouble concentrating.

Less common side effects of Suboxone include:

- vomiting
- mild dizziness;
- tingling
- muscle cramps;
- distress and irritability; or,
- fever.

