Risk of Accidental Exposure in Children: There is an increased chance of child exposure to buprenorphine resulting from this medical intervention. However, this should be viewed in a wider health perspective. Most medications prescribed by ED (hypoglycemics, CCBs, BBs, cholchicine, other opioids, etc) are dangerous in exploratory ingestions and many of these are on the “one pill can kill” list for kids. It is likely the adults who will receive a Suboxone Starter Pack have opioids in the home already. In fact, the study is attempting to trade illicit use (e.g. heroin/fentanyl) for a safer opioid which should lead to improved adult supervision of children and reduce risk of parental death by overdose. The benefits to families of treating the disease appear to outweigh the risks.

Risks from Opioid Withdrawal: Opioid withdrawal symptoms which include tearing up, muscle aches, agitation, trouble falling and staying asleep, excessive yawning, anxiety, nose running, sweats, racing heart, hypertension, nausea and vomiting, diarrhea, stomach cramps, depression and drug cravings. Symptoms of withdrawal will be managed with buprenorphine. Participants will be educated about opioid withdrawal with a fact sheet that includes a brief list of coping strategies. If participants still experience opioid withdrawal after buprenorphine induction, research staff will cue the participant to use coping strategies. Clinical support will be provided by addiction psychiatrists at the ATP.

Risks from Research Assessments: The assessments being used in this study (e.g. measures of substance use, symptoms, information about patient history, and urine assessments) may cause some discomfort, boredom, anxiety or fatigue. Participants will be advised that they can take a break, refuse to answer question(s), or end the study session if they become uncomfortable in any way. Additionally, psychiatrists experienced in the treatment of addiction, will be present or rapidly available via pager for emergency consultation at any time.

Risk Related to Confidentiality: This research involves monitoring and treatment of patients who use illicit opioids. Participants may engage in other illegal drug use activities. Maintaining confidentiality is an area of utmost importance for this population.

Protections Against Risks

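### The buprenorphine side-effect question at 3 and 6 months does not ask when a symptom occurred, and 7 of its 12 symptoms are also on the protocol's own opioid-withdrawal list

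*Combined protocol and SAP*

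**What the plan says.** The follow-up questions are set out in the questionnaire part of Methods and Procedures, under the 3 and 6 month heading. Item 1 asks about any further prescribed buprenorphine since the ED. Item 2 asks about enrollment with a prescriber in the last 30 days, and item 3 asks why the person is not receiving it. A No to item 1 skips item 2 only, so that person goes on to item 3 and then item 4.

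Item 4 asks: "Since you started receiving treatment in the ED have you experienced any of the following side effects of buprenorphine". The symptoms offered are: "Constipation, diarrhea, stomach pain, nausea, vomiting, brain fog, sleeping too little, tiredness, sexual problems, feeling depressed or down, feeling anxious, headache". The only follow-up is: "How much discomfort did this cause you on a scale 1 to 5 where 1 is mild and 5 is severe".

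Two other lists in Risks/Benefits bear on this:

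- The paragraph on risks from opioid withdrawal names "tearing up, muscle aches, agitation, trouble falling and staying asleep, excessive yawning, anxiety" and then "nose running, sweats, racing heart, hypertension, nausea and vomiting, diarrhea, stomach cramps, depression and drug cravings".
- The section on risks from buprenorphine gives eight common effects, among them "redness, pain, or numbness in your mouth". A further six stand under "Less common side effects of Suboxone include".

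The Buprenorphine Induction section gives every participant a three-day Starter Pack. Nothing beyond those three days is guaranteed to have been taken.

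**The concern.** The item labels whatever is reported as an effect of the drug, over a window that runs from the ED visit to the call. Several things other than the drug can produce the same symptoms in that window:

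- **Induction.** Some participants start Suboxone while in withdrawal. The others are told to wait for withdrawal symptoms before the first films. Withdrawal near the start of the window is expected even in people who take everything as instructed.
- **Stopping treatment.** The Withdrawal Procedures section keeps people who leave the bridge clinic in the study, and they are paid for follow-up whether or not they are in treatment. A person who stopped and then went through withdrawal is asked the same question.

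At stake is how well a tolerability summary from item 4 can be interpreted. Time on treatment is also expected to differ between the groups, since that is how the bridge clinic is meant to work. Misattributed symptoms could therefore differ between groups as well. Timing that was not asked during the call cannot be recovered later.

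**Working it through.** The plan gives no figure on this point, so the check sets item 4 beside the protocol's two lists.

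**Matching rule (base).** Stomach pain is paired with stomach cramps and with abdominal pain, brain fog with trouble concentrating, and sleeping too little with trouble sleeping and with insomnia.

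| Item 4 symptom | Withdrawal list | Suboxone list |
|---|---|---|
| Constipation | no | common |
| Diarrhea | yes | no |
| Stomach pain | yes | common |
| Nausea | yes | common |
| Vomiting | yes | less common |
| Brain fog | no | common |
| Sleeping too little | yes | common |
| Tiredness | no | common |
| Sexual problems | no | no |
| Depressed or down | yes | no |
| Anxious | yes | no |
| Headache | no | common |

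**Counts.** Both lists 4, withdrawal only 3, Suboxone only 4, neither 1 (4 + 3 + 4 + 1 = 12). On the withdrawal list: 4 + 3 = 7, and 7/12 = 58%.

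**Sensitivity to matching.**

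- Strict (cramps are not the same as stomach pain; brain fog is not the same as trouble concentrating): 6/12 = 50% on the withdrawal list, 3 of them withdrawal only.
- Lenient (distress and irritability taken to cover depressed and anxious): 7/12 = 58% on the withdrawal list, 1 of them withdrawal only (diarrhea).

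**Coverage of the Suboxone list.** Under base matching item 4 leaves out 3 of the 8 common effects (sweating, mouth symptoms, feeling drunk) and 5 of the 6 less common ones (mild dizziness, tingling, muscle cramps, distress and irritability, fever). That is 3 + 5 = 8 of 14. Strict matching also loses trouble concentrating (9 of 14). Lenient matching recovers distress and irritability (7 of 14). Of the three missing common effects, sweating is itself on the withdrawal list, so only mouth symptoms and feeling drunk would help to separate drug from withdrawal.

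**Can existing data supply the timing?**

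- Item 1 is Yes after any later prescription, however brief. It says nothing about non-prescribed buprenorphine, and a No still leaves the Starter Pack.
- Item 2 covers the last 30 days of a three- or six-month window.
- The urine test for buprenorphine reflects use near the visit.

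None of these dates a symptom. For a person who took only the Starter Pack, the guaranteed exposure is 3 days out of roughly 90 or 180 (3/90 = 3%; 3/180 = 2%).

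**The case against.** The strongest reply is that no planned result rests on item 4. It is not part of the primary outcome or among the secondary outcomes named under Objectives. Statistical Considerations plans an analysis of illicit opioid use only, and adverse events have their own reporting route and six-monthly review. This stands, and it limits how much weight the point can carry.

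Three further replies also stand:

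- Four of the seven overlapping symptoms (nausea, vomiting, stomach pain, sleeping too little) are listed Suboxone effects, so a side-effect question should include them. The fault is the missing timing, not their presence.
- Asking everyone is right. All participants receive the Starter Pack, and people who stopped because of early intolerance are the ones the item should reach.
- The Suboxone list is a risk disclosure, not a specification for data collection. A follow-up questionnaire is attached to the protocol but is not among the documents available, so it cannot be confirmed that the omitted effects are asked nowhere.

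A reader might infer that item 4 cannot separate drug effects from withdrawal at all. The documents do not support that. Constipation, brain fog, tiredness and headache are on the Suboxone list only, and items 1 and 2 with the urine result give a coarse split.

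A reader might also infer a false difference in side-effect rates between the groups of some stated size. The documents give no share off treatment by group, no rate of withdrawal symptoms, no scoring rule and no planned comparison. Any such figure would rest wholly on assumed inputs. Withdrawal around induction is also expected in both groups, which would dilute a difference.

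**Conclusion.** The point holds in a limited form. Seven of 12 symptoms (six under strict matching) are on the protocol's own withdrawal list, and three of the seven are not on its Suboxone list (one under lenient matching). With no question on timing or concurrent use, and with people asked who had only the Starter Pack, most positive answers on the overlapping symptoms cannot be attributed to drug or to withdrawal. The same applies to any pooled count of people with at least one side effect.

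This rests on reading the item as printed, with no timing question in the unseen attachment, and on the matching shown above. The gaps in coverage are secondary. This is a minor improvement to an exploratory item, and no size of bias can be stated from the documents.

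**What to change.** Keep asking item 4 of everyone. For each symptom reported, add one prompt on when it occurred: around the first doses, while taking buprenorphine (Starter Pack included), or after stopping. Tabulate by that timing. Call only on-drug symptoms possible side effects, and report those after stopping separately as symptoms off treatment. Show the first-dose category in its own row, because the protocol expects withdrawal then and attribution stays open.

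Do not define who was exposed by item 1 or by a single urine result. Either would move people who had only the Starter Pack into an unexposed group and hide early intolerance.

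Optionally, add the two common Suboxone effects that are missing from item 4 and absent from the withdrawal list: mouth symptoms and feeling drunk.

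Introduce the wording at all sites at the same time and record the form version. Sites define the groups, so a staggered change would confound wording with group. The pending amendment for the two additional hospitals is a natural occasion.

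The cost is a questionnaire amendment, about a minute more per call, imperfect recall of timing over months, and two form versions, since one site is already enrolling.
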